22.6 Causality

The investigator will assess the relationship of an adverse event to the surgical intervention. If possible, the investigator should distinguish the relationship between the event and (a) the surgical procedure and (b) the investigational intervention (implant of Edwards SAPIEN 3 valve). Causality will be defined as follows:

A. Probable

Adverse events that, after careful medical evaluation, are considered with a high degree of certainty to be related to the surgical intervention

The following characteristics will apply:

- 1. A reasonable temporal relationship exists between the event and the surgical intervention, and
- The event is a known reaction to the surgical intervention and cannot be explained by an alternative etiology commonly occurring in the population/individual.

B. Possible

Adverse events that, after careful medical evaluation, do not meet the criteria for a probable relationship to the surgical intervention, but for which a connection cannot be ruled out with certainty.

The following characteristics will apply:

- 1. The event occurs after surgical intervention, and
- The event is not a known reaction to surgical intervention, but cannot be explained by a commonly occurring alternative etiology.

C. Unlikely

Adverse events that, after careful medical evaluation, do not meet the criteria for a possible or probable relationship to surgical intervention and for which a connection is unlikely.

The following characteristics will apply:

- The event does not follow a reasonable temporal sequence from administration of the surgical intervention, or
- 4. May have been produced by environmental factors, and there is no apparent pattern of response to the surgical intervention.

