4.0 STUDY DESIGN

Baylor Scott & White Research Institute

Confidential

This is a multi-center, prospective feasibility study. The study cohort will comprise all consecutive subjects undergoing mitral valve replacement with the Edwards SAPIEN 3 heart valve by a standardized minimally invasive surgical approach at investigational centers and will consist of up to 30 subjects. Subjects will undergo follow-up visits at 30 days, 6 months and 12 months post procedure.

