6.0 STUDY OBJECTIVES

6.1 **Primary Outcome Measures:**

- a. Primary objective(s)
 - Primary safety endpoints:

- o Technical success at exit from cath lab/OR
- Device success at 30 days
- Procedural success at 30 days

Technical Success:

- Alive, with
- Successful access, delivery and retrieval of the device delivery system, and
- Deployment and correct positioning (including repositioning/recapture if needed) of the single intended device, and
- No need for additional unplanned or emergency surgery or re-intervention related to the device or access procedure

Device Success:

- Alive and stroke free, with
- Original intended device in place, and
- No additional surgical or interventional procedures related to access or the device since completion of the original procedure (i.e., exit from the cath lab/OR), and
- Intended performance of the device:
 - Structural performance: No migration, embolization, detachment, fracture, hemolysis, thrombosis (including reduced leaflet motion) or endocarditis, etc, and
 - Hemodynamic performance: Maintenance of relief of stenosis or insufficiency without producing the opposite (Stenosis = MVA < 1.5cm2 and MV gradient > 5mmHg, Insufficiency = MR >1+), and
 - Absence of para-device complications (e.g., PVL > mild, need for a PPM, erosion, Annular rupture or AV Groove disruption, LVOT gradient increase > 10mmHg)

Procedural Success:

Device success, and

- No device or procedure related SAE's (Life threatening bleed; major vascular or cardiac structural complications requiring unplanned reintervention or surgery; stage 2 or 3 AKI (includes new dialysis); MI or need for PCI/CABG; severe HF or hypotension requiring IV inotrope, ultrafiltration or mechanical circulatory support; prolonged intubation (> 48 hours)
- •
- 6.2 Secondary objective(s)
 - Device Success (at 6 months and 1 year)

- Subject success 1 year Device Success:
- Alive and stroke free, with
- Original intended device in place, and
- No additional surgical or interventional procedures related to access or the device since completion of the original procedure (i.e., exit from the cath lab/OR), and
- Intended performance of the device:
 - Structural performance: No migration, embolization, detachment, fracture, hemolysis, thrombosis (including reduced leaflet motion) or endocarditis, etc, and

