14.4.3 Twelve Month Follow-Up Visit

The following data will be collected for all study subjects at 1 year (365 days) +60 days.

A. Systems:

- C. Pertinent physical examination [includes blood pressure, weight, major systems findings] including clinical assessment for Stroke and/or TIA;
- D. Medications given for cardiovascular effect including anti-platelet/anti-thrombins
- E. Adverse Event assessment

B. Cardiac:

- F. NYHA classification
- G. Standard 12-lead ECG
- H. Chest X-ray examination
- I. Transthoracic echocardiogram (TTE)

C. Clinical Laboratory Tests:

- J. CBC and platelet count
- K. Complete metabolic panel
- L. B-type natriuretic peptide (BNP)
- M.Plasma free hemoglobin
- N. Haptoglobin.
- O. PT/INR (if applicable)

D. Functional Assessments:

- P. 6MWT
- Q. QOL: KCCQ

SITRAL

Baylor Scott & White Research Institute 15.0 STUDY DATA MONITORING AND DATA AND SAFETY MONITORING BOARD

The purpose of the monitoring plan is to facilitate compliance with GCP guidelines (GCP 5.18.1), FDA guidelines and FDA regulations (21 CFR 812). The monitoring plan for this study includes use of monitoring services and institution of a Data and Safety Monitoring Board. A Data Safety and Monitoring Board (DSMB) will be constituted for this study to provide additional safety review. The DSMB is an independent advisory group of experts with a mandate to periodically review and evaluate safety and evaluate data for continuing validity.

The DSMB will be responsible for assuring that research subjects are not exposed to unnecessary or unreasonable risks. Ongoing responsibilities of the DSMB will be to evaluate the progress of the study, including periodic assessments of adverse events and serious adverse events. The DSMB will report on the safety and scientific progress of the study.

On site monitoring will be completed at regular intervals at each site commensurate with enrollment of the first subject and completion of the index procedure. As an electronic data capture system will be used to collect the data, the data entered into the database will be remotely reviewed to evaluate for potential safety issues such as unanticipated adverse device effects. Compliance with the study milestones for each enrolled subject will be reviewed, as well. Sites will be contacted for source information as indicated.

Reports from each monitoring visit will be provided to the site Investigator and the sponsor at completion of the monitoring.

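### Procedural success at 30 days depends on whether listed complications are graded device- or procedure-related; the text available has nobody confirm the investigator's grade and plans no all-cause count beside it.

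*Combined protocol and SAP*

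**What the plan says.** Section 6.1 lists "Procedural success at 30 days" among the primary safety endpoints. It has two parts. The first is device success, which opens with "Alive and stroke free, with" and so counts death and stroke whatever their cause. The second begins "No device or procedure related SAE's (Life threatening bleed" and goes on to major vascular or cardiac structural complications needing unplanned reintervention, stage 2 or 3 kidney injury, MI or coronary revascularisation, severe heart failure or hypotension needing support, and intubation beyond 48 hours.

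Section 22.6 assigns the causality judgement: "The investigator will assess the relationship of an adverse event to the surgical intervention". The grades are Probable, Possible and Unlikely. Possible covers events "for which a connection cannot be ruled out with certainty". No section says which grades make an event related for the endpoint.

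Other parties have other tasks. The DSMB (Section 15.0) makes "periodic assessments of adverse events and serious adverse events"; adjudicating endpoints or causality is not among its stated duties. The core lab (Section 17.0) reads echocardiograms and CT scans. Sponsor data review (Section 24.1) looks for inconsistent or missing data and adverse events. The case review in Section 9.0 concerns eligibility.

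The design is one treated cohort: "The study cohort will comprise all consecutive subjects undergoing mitral valve replacement with the Edwards SAPIEN 3 heart valve" (Section 4.0), up to 30 subjects. Section 23.0 plans descriptive percentages and plots.

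**The concern.** If relatedness is a condition that each event must meet, a listed complication fails the subject only when it is graded related, and the grade comes from an investigator at the site whose result is being scored. A listed event graded unrelated can leave the rate unchanged or raise it; it cannot lower it. There is no control arm in which the same grading habit would appear and partly cancel.

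The grades do not fully constrain the judgement. Probable requires a known reaction that has no common alternative cause. Possible, by its listed characteristics, requires an event that is not a known reaction. A known complication with a plausible alternative cause, such as kidney injury in a subject with reduced baseline renal function, meets neither set, so discretion decides.

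What is at stake is how a primary safety percentage is read. Two sites with identical outcomes could report different procedural success, and the planned output would not show it.

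**Working it through.** The plan states no expected success rate, event rate or precision target, so there is no figure of its own to reproduce.

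**Step 1: weight of one subject.** With n = 30 (the maximum in Section 4.0), one subject is 100/30 = 3.3 points.

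**Step 2: when a grade changes the result.** Procedural success is nested in device success. Grading an event unrelated changes the outcome only if the subject meets device success and has no other listed event graded related.

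**Step 3: formula.** All three inputs are assumptions, because the documents give none of them:
- d = share of subjects meeting device success, 0.6 to 0.8
- p = share of subjects with at least one listed event by day 30, 0.2 to 0.5, taken as independent of device success
- u = share of those subjects whose listed events are all graded unrelated, 0.1 to 0.3

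All-cause rate = d(1 − p). Related-only rate = d(1 − p(1 − u)). Gap = d × p × u.

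| | d | p | u | All-cause | Related-only | Gap |
|---|---|---|---|---|---|---|
| Low | 0.6 | 0.2 | 0.1 | 48.0% | 49.2% | 1.2 points |
| High | 0.8 | 0.5 | 0.3 | 40.0% | 52.0% | 12.0 points |

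In subjects, this is 0.012 × 30 = 0.36 to 0.12 × 30 = 3.6 of 30. Leaving out d would give 0.2 × 0.1 = 2 to 0.5 × 0.3 = 15 points, which is too large because it ignores the nesting. If listed events cluster in subjects who already fail device success, the gap is smaller than the table shows.

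**Step 4: example with assumed counts.** Of 30 subjects, 24 meet device success. Eight of the 24 have a listed event, and two of those eight have only events graded unrelated.
- Related-only: 24 − 6 = 18, so 18/30 = 60.0% (exact 95% CI 40.6-77.3%)
- All-cause: 24 − 8 = 16, so 16/30 = 53.3% (34.3-71.7%)

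The gap is 2/30 = 6.7 points. Both rates come from the same subjects, so overlap of the intervals does not make the gap a chance finding; it follows entirely from the counting rule.

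**The case against.** **The list may itself define what is related.** The parenthesis in Section 6.1 can be read as naming the events that count as device- or procedure-related. On that reading they fail the subject automatically and the Section 22.6 grade plays no part. No section states that the grade feeds the endpoint. This stands as a genuine ambiguity. It narrows the point but does not remove it, since the text does not settle which reading applies.

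**Nobody else is an inference from silence.** Section 22.6 says the investigator, without saying treating or alone. This stands: the point is that no second assessor appears in the text available, not that one is ruled out.

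**The gap is not a measure of bias.** Some events graded unrelated will have been graded correctly, and against a truly related rate misgrading can go either way. A reader might infer that the endpoint is biased upward by the whole gap. The documents do not support that: the gap is the difference between two endpoint definitions, and an unknown part of it is attribution error.

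**An alternative cause does not by itself earn the grade Unlikely.** Section 22.6 asks for an unreasonable time sequence, or for possible environmental causes with no pattern of response to the surgery. Kidney injury is assessed up to 7 days and peri-procedural MI within 72 hours (Appendix 2), close to the operation. This limits how many events could be graded unrelated. It does not help with events that fit no grade.

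**The study is a small descriptive feasibility study.** There is no test or performance goal, serious events are reportable whether expected or not (Section 22.7), and the DSMB reviews safety. This stands. No type I error is involved, and counting death and stroke from any cause but other complications by relatedness is a permissible design choice. The percentage is nevertheless the planned result, so its dependence on attribution should be visible.

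**Conclusion.** The point holds in a limited form. Unless the listed events are meant to count automatically, the procedural success rate depends partly on attribution that no one is stated to confirm. Each subject who otherwise meets device success, has no other related listed event, and has a listed event graded unrelated adds 3.3 points of 30.

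The total size is unknown. Under the assumed ranges the all-cause and related-only rates differ by about 1 to 12 points; that range rests on device success being independent of the listed events, and it is not all bias.

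Two stronger inferences should be resisted. One is that the investigator controls the endpoint: death and stroke count whatever the cause, the images are read by a core lab, and Section 6.1 may not use the grade at all. The other is that any statement about safety must be withheld unless the all-cause rate supports it: the plan has no decision rule to which such a condition could attach. This is a cheap improvement in reporting, not an obstacle to running the study.

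**What to change.** In Sections 6.1 and 23.0, pre-specify that procedural success is also reported with every listed event through day 30 counted as a failure whatever the investigator's grade. Show it beside the related-only rate, both with exact 95% confidence intervals. In the same edit to Section 6.1, state whether the listed events count automatically and, if not, which grades count as related.

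Sections 6.1 and 22.9 must also be reconciled. The list of anticipated events in Section 22.9 says that temporary medical or mechanical hemodynamic support around the operation is not an adverse event, whereas Section 6.1 counts severe heart failure or hypotension needing inotropes or mechanical support as a failure. As written, some listed events might never be recorded, and neither rate would then be complete.

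The cost is a few sentences and one extra percentage; no adjudication committee is needed. The small downside is that the added rate will be equal to or less favourable than the related-only rate. The change does not touch the separate relatedness conditions on reintervention within technical success and device success.

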22.9 Anticipated or Potential Adverse Events

The list below provides anticipated or potential adverse events that may occur during the study. The potential adverse events are those that are expected to occur during the study because they are associated with the surgical procedure, stress-induced tests (e.g. TEE/TOE, TTE, MSCT scan, exercise tolerance, etc.), or the heart failure population over time. It is anticipated that subjects may require temporary medical and/or mechanical hemodynamic support in the peri and/or early post-op period. These events are not considered adverse events.

- Abnormal Lab values
- Allergic Reaction to Anesthetic, Anticoagulant Therapy, Contrast or Cobalt Chromium
- Anaphylactic Shock or Toxic Reaction
- Anemia
- Angina
- Annulus Rupture/ A-V Groove Disruption
- Aortic Valve Impairment/Damage
- Arrhythmias
- Atrial Fibrillation
- Atrio-ventricular Node Block
- A-V fistula or pseudo-aneurysm
- Bleeding diathesis
- Cardiac Arrest
- Cardiac Failure or Decompensation
- Cardiac Perforation
- Cardiac Tamponade/ Pericardial Effusion
- Cardiogenic Shock
- Chordal Rupture

- Conduction System Injury (defect) which may require pacemaker
- Conversion to Open Sternotomy
- Coronary Artery Obstruction
- Death
- Dissection, Any Vessel
- Dyspnea
- Edema
- Electrolyte Imbalance
- Electro-mechanical Dissociation
- Embolization including air, particulate, calcific material, or thrombus
- Emergent PCI
- Emergent Cardiac Surgery
- Endocarditis
- Esophagus Irritation/Perforation (TEE related)
- Fever
- Frame Strut Fracture
- GI Bleeding
- Heart Failure

SITRAL

Baylor Scott & White Research Institute

- Hematoma
- Hemolysis / Hemolytic Anemia
- Hemorrhage require transfusion/surgery
- Infection at the access site
- Inflammation
- Leaflet tearing
- Left Ventricle Failure
- Local and Systemic Infection
- LVOT Obstruction
- Mal-positioning of Prosthesis
- Multi-system Failure
- Myocardial Infarction
- Myocardial Ischemia
- Pacemaker Implantation
- Pannus Formation
- Papillary Muscle Damage
- Peripheral Ischemia
- Pleural effusion
- Pneumonia
- Prosthesis Dislodgement/Embolization
- Prosthesis Leaflet Entrapment

- Prosthesis Migration
- Prosthesis Paravalvular Leak
- Prosthesis Regurgitation
- Prosthetic Valvular Endocarditis
- Prosthetic Valvular Thrombosis
- Pulmonary Edema
- Pulmonary Vein Obstruction
- Reintervention or reoperation
- Renal Failure or Insufficiency
- Respiratory Failure
- Retroperitoneal Bleed
- Septicemia

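### The Possible grade in Section 22.6 is narrower than its own lead-in, and Section 6.1 does not say which events count as related for procedural success

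*Combined protocol and SAP*

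**What the plan says.** Section 22.6 asks the investigator to grade each adverse event as Probable, Possible or Unlikely. Each grade has a lead-in sentence and a list of characteristics.

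- **Probable** needs a reasonable temporal relationship and that "The event is a known reaction to the surgical intervention and cannot be explained by an alternative etiology commonly occurring in the population/individual".
- **Possible** is, by its lead-in, for events that miss Probable "but for which a connection cannot be ruled out with certainty". Its list requires that the event comes after surgery and that "The event is not a known reaction to surgical intervention, but cannot be explained by a commonly occurring alternative etiology".
- **Unlikely** is, by its lead-in, for events that "do not meet the criteria for a possible or probable relationship to surgical intervention and for which a connection is unlikely". Its list requires either an unreasonable temporal sequence or that the event "May have been produced by environmental factors, and there is no apparent pattern of response to the surgical intervention".

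Section 6.1 defines procedural success as device success plus "No device or procedure related SAE's (Life threatening bleed; major vascular or cardiac structural complications requiring unplanned reintervention or surgery", followed by further event types. One of these is "severe HF or hypotension requiring IV inotrope, ultrafiltration or mechanical circulatory support". Section 6.1 does not cite Section 22.6.

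Section 22.9 (Anticipated or Potential Adverse Events) says that subjects may need "temporary medical and/or mechanical hemodynamic support in the peri and/or early post-op period. These events are not considered adverse events".

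Section 23.0 plans descriptive percentages and plots only.

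**The concern.** A known complication of surgery with a plausible competing cause is a common causality question after high-risk valve surgery. Section 22.6 gives two answers to it. The lead-in makes the event Possible; the list shuts it out of Possible, and it fits neither other list. Two sites with the same facts could record different grades, and neither would know whether Possible counts as related for the endpoint.

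Procedural success at 30 days is one of three primary endpoints, and the study is multi-center. The investigator assigns the grade. Section 15.0 gives the DSMB periodic review of adverse events but states no role in settling relatedness. The only other definition of relatedness to the procedure for an adverse outcome, in Appendix 2, covers death alone.

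For the hemodynamic-support component there is a prior question: whether an event exists to be graded at all. What is at stake is whether the reported percentage means the same thing at every site.

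**Working it through.** The plan gives no figure to reproduce here, so the check is of the wording.

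**1. Inputs from Section 22.6.** For an event after surgery, take four yes/no facts: T, reasonable timing; K, known reaction to surgery; A, common alternative etiology; E, environmental cause with no pattern of response. That gives 2 × 2 × 2 × 2 = 16 combinations.

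**2. The lists as rules.**
- Probable: T and K and not A.
- Possible: not K and not A.
- Unlikely: not T, or E.

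**3. Apply the lead-ins as well.** Possible is only for events that miss Probable, and Unlikely only for events that miss both. Taken in that order, the 16 combinations fall as 2 Probable, 4 Possible, 8 Unlikely and 2 with no grade (2 + 4 + 8 + 2 = 16). No combination holds two grades.

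**4. Where the gap lies.** With reasonable timing and no environmental cause:

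| Known reaction | Common alternative | List met | Possible lead-in |
|---|---|---|---|
| yes | no | Probable | not applicable |
| no | no | Possible | open |
| yes | yes | none | open |
| no | yes | none | open |

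The last two rows are the ungraded ones. These are combinations of facts, not event frequencies.

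**5. Does the gap reach the endpoint's events?** The parenthesis in Section 6.1 has six event groups. Each has a counterpart on the anticipated list in Section 22.9: hemorrhage; vascular trauma or annulus rupture; renal failure; myocardial infarction or emergent PCI; heart failure or cardiogenic shock; and respiratory failure, the nearest match to prolonged intubation. Treating that list as known reactions is an assumption, because it also covers events from study tests and from the heart failure population.

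**6. Scope.** Appendix 2 confines AKI to 7 days and peri-procedural MI to 72 hours, where competing causes are fewer. The exclusions in Section 5.3 remove several more. Later bleeding, spontaneous MI and later heart failure remain. Death, stroke, paravalvular leak and LVOT gradient carry no relatedness condition and are untouched.

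**7. Hemodynamic support.** An SAE must first be an adverse event. If early temporary support is not one (Section 22.9), a subject on an inotrope or mechanical support soon after surgery may have nothing to grade. Section 6.1 lists severe heart failure or hypotension requiring that support as a failure.

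**8. Size.** At the maximum n of 30, one affected subject with no other failing component moves the rate by 1/30 = 3.3 points. For an assumed 0, 1, 2 or 3 such subjects the shift is 0, 3.3, 6.7 or 10.0 points. For scale, an assumed 24/30 is 80.0% with exact (Clopper-Pearson) 95% interval 61.4 to 92.3, a width of 30.9 points; 23/30 is 76.7% (57.7 to 90.1).

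**The case against.** The strongest reply is that the endpoint may not use the grades at all. Section 6.1 does not cite Section 22.6, and its parenthesis can be read as naming the events that count, whatever their grade. On that reading the grading gap has no effect on procedural success. This stands as a limit on the point but does not remove it: the word related is in the definition, and nothing says which reading applies.

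Even if the grades are used, several things must coincide: the event is treated as a known reaction, a common alternative exists, and the subject fails on nothing else. Structural complications needing reintervention will often already fail device success. A one-subject shift is well inside sampling error, and no threshold is tested. All of this stands.

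On hemodynamic support, one could say that expected temporary support is one thing and severe heart failure or hypotension is another. That may be the intention, but no passage draws the line, and the same treatments appear in both places.

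A reader might also infer that the grades overlap, since on the lists alone 4 of the 16 combinations meet two. The documents do not support this: the lead-ins already rank the grades and resolve all four. Nor does the fact that no known reaction can meet the Possible list add anything; it restates that list's own condition.

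**Conclusion.** The point holds in limited form. The Possible list is narrower than, and inconsistent with, its lead-in, and leaves timely events with a common alternative etiology and no environmental cause without a grade. Section 6.1 does not say which grades count as related, or whether its listed events count regardless. Sections 22.9 and 6.1 treat early hemodynamic support differently.

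The effect on procedural success is conditional, and neither its size nor its direction can be derived, because the documents give no event rates. A reader might infer that the reported rate will be biased upward, or that the endpoint is unusable; the documents support neither. The defect still merits correction: followed as written, the list and the support exclusion could leave out or misclassify events that a primary endpoint names.

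**What to change.** 1. **Section 22.6.** Align the Possible list with its lead-in: any post-surgery event that is not Probable and whose connection cannot be ruled out, including a known reaction with a competing etiology. Add to Unlikely a timely event whose documented alternative cause makes a connection unlikely. Because little can be ruled out with certainty, Possible should give way where timing, an environmental factor or a documented alternative cause makes a connection unlikely; otherwise it would absorb Unlikely. No new grading order is needed.
2. **Section 6.1.** State either that all listed events count regardless of grade, or that Probable and Possible both count as related, citing Section 22.6.
3. **Section 23.0.** If grades are used, also report procedural success with every listed event through day 30 counted as a failure. If the two percentages agree, grading did not matter.
4. **Sections 22.9 and 6.1.** Reconcile the passages on early hemodynamic support. Which rule governs is for the sponsor and clinicians to decide.

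The cost is wording in three sections and at most one further descriptive percentage, with no added visits, tests or staff. The downside is a possibly slightly less favourable rate, since some events with a competing cause would count as related. Some investigator judgement will remain between Possible and Unlikely; the grade-independent percentage shows how much it matters.
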